13.2.7 Safety Reporting

Adverse events/SAEs will be assessed at all study visits as outlined in the Schedule of Study Procedures and Assessments (see Section 21.3).

Adverse events/SAEs are to be recorded on the AE page of the eCRF. Each event should be recorded separately.

Any SAE, including death due to any cause, which occurs during this study, whether or not related to the investigational product, must be reported immediately (within 24 hours of the study site's first knowledge of the event). All SAEs must be reported via the Electronic Data Capture (EDC) system by completing the relevant electronic Case Report Form (eCRF) page(s) in English. For instances in which the EDC may become unavailable, SAEs must be reported using the back-up paper SAE Report Form to meet the 24-hour timeline requirement (for contacts and instructions refer to the SAE Report Form). Once the EDC becomes available, the site must enter all SAE data as reported on the back-up paper SAE Report Form on the applicable eCRF pages.

The initial SAE information reported on the applicable eCRF pages (or back-up SAE Report Form, if applicable) must at least include the following:

1. Protocol Number
2. Subject identification number and demographics (gender, age at onset of event, and/or date of birth)
3. Investigational product exposure
4. Medical Term for Event (Diagnosis preferably)
5. Description of the (S)AE, including:
 - Date of onset
 - (S)AE treatment (drug, dose, route of administration)
 - Causal relationship by the Investigator
 - Measures taken (i.e., action taken regarding investigational product in direct relationship to the AE)
6. Seriousness criteria (i.e., death, life-threatening, or other criterion)

7. Cause of death
8. Autopsy findings (if available)
9. Name, address, fax number, email, and telephone number of the reporting Investigator (for paper SAE Report Forms)

13.2.8 Medical Device Safety Reporting

The IP kit contains the BAXJECT device. All Serious Injuries and Unexpected Adverse Device Events must be reported to the sponsor as an SAE in the same process as described above.

Serious injury is defined as:

1. Life-threatening injury or illness results in permanent impairment/ damage to body function/ structure
2. Requires medical or surgical intervention to preclude permanent impairment/ damage to body function/ structure

13.3 Urgent Safety Measures

An urgent safety measure is an immediate action taken, which is not defined by the protocol, in order to protect subjects participating in a clinical trial from immediate harm. Urgent safety measures may be taken by the sponsor or clinical investigator, and may include any of the following:

- Immediate change in study design or study procedures
- Temporary or permanent halt of a given clinical trial or trials
- Any other immediate action taken in order to protect clinical trial participants from immediate hazard to their health and safety

The investigator may take appropriate urgent safety measures in order to protect subjects against any immediate hazard to their health or safety. The measures should be taken immediately and may be taken without prior authorization from the sponsor. In the event(s) of an apparent immediate hazard to the subject, the investigator will notify the sponsor immediately by phone and confirm notification to the sponsor in writing as soon as possible, but within 1 calendar day after the change is implemented. The sponsor will also ensure the responsible ethics committee is notified of the urgent measures taken in such cases according to local regulations.

13.4 Untoward Medical Occurrences

Untoward medical occurrences occurring before the first exposure to IP are not considered AEs (according to the definition of AE, see Section 13.2). However, each **serious** untoward medical occurrence experienced before the first IP exposure (i.e., from the time of signed informed consent up to but not including the first IP exposure) will be described on the AE CRF (and SAE Report Form if eCRF is not available). These events will not be considered as SAEs and will not be included in the analysis of SAEs.

For the purposes of this study, each non-serious untoward medical occurrence experienced by a subject undergoing study-related procedures (e.g., during blood sampling) before the first IP exposure will be recorded on the AE CRF; these events will not be considered as AEs and will not be included in the analysis of AEs.

13.5 Non-Medical Complaints

A non-medical complaint (NMC) is any alleged product deficiency that relates to identity, quality, durability, reliability, safety and performance of the product but **did not result in an AE**. NMCs include but are not limited to the following:

1. A failure of a product to exhibit its expected pharmacological activity and/or design function, e.g., reconstitution difficulty
2. Missing components
3. Damage to the product or unit carton
4. A mislabeled product (e.g., potential counterfeiting/tampering)
5. A bacteriological, chemical, or physical change or deterioration of the product causing it to malfunction or to present a hazard or fail to meet label claims

Any NMCs of the product will be documented on an NMC form and reported to the sponsor within 1 business day. If requested, defective product(s) will be returned to the sponsor for inspection and analysis according to procedures.

13.6 Medical, Medication, and Non-Drug Therapy History

At screening, the subject's medical history will be described for the following body systems including severity (defined in Section 13.2.5) or surgery and start and end dates, if known: eyes, ears, nose, and throat; respiratory; cardiovascular; gastrointestinal; musculoskeletal; neurological; endocrine; hematopoietic/lymphatic; dermatological; and genitourinary.

The historical ABR including treated and untreated bleeding episodes in the 12 months prior to study enrollment based on medical records should also be recorded in the eCRF. Only the treated bleeds will be the basis for inclusion in the study.

All medications taken and non-drug therapies received from 4 weeks before enrollment until completion/termination will be recorded on the concomitant medications and non-drug therapies CRFs.

Any prior use of any pegylated medication (name of drug, indication, and dates of use), at any time in the past, will be recorded on the eCRF.

13.7 Physical Examinations

At screening and subsequent study visits (as described in the schedule in Section 21.2), a physical examination will be performed on the following body systems: general appearance, head and neck, eyes and ears, nose and throat, chest, lungs, heart, abdomen, extremities and joints, lymph nodes, skin, and neurological. At screening, if an abnormal condition is detected, the condition will be described on the medical history CRF. At screening, the Karnofsky performance score will be assessed.

At study visits, if a new abnormal or worsened abnormal pre-existing condition is detected, the condition will be described on the AE CRF. If the abnormal value was not deemed an AE because it was due to an error, due to a preexisting disease (described in Section 13.2.3), not clinically significant, a symptom of a new/worsened condition already recorded as an AE, or due to another issue that will be specified, the investigator will record the justification on the source record.

13.8 Clinical Laboratory Parameters

All assessments will be performed at a central laboratory, according to the laboratory manual.

At all laboratory assessments subjects must not be actively bleeding. In addition to the laboratory assessments planned in the protocol, appropriate clinical laboratory testing should be performed whenever clinically indicated.

Details on the visits and timing of blood sampling for the laboratory parameters are provided in Section 21.2 and Section 21.3.

13.8.1 Screening Laboratory Parameters

13.8.1.1 Blood Type

For subjects who do not have documentation of their blood type in their medical record, blood ABO blood type will be measured locally at screening.

13.8.1.2 Genetics and HLA-Genotype

FVIII gene mutation analysis and HLA genotype will be analyzed at screening. If results of FVIII gene mutation analysis and HLA genotype are already available at the study site, they will be provided to the sponsor and a reanalysis will not be required in those subjects.

13.8.1.3 Pregnancy Test

A pregnancy test should be performed as appropriate (serum pregnancy test in females of child-bearing potential if no urine sample is available). The pregnancy test might be repeated during the study in countries where mandated by national law.

13.8.1.4 CD4 Count

At screening only, CD4 levels will be determined in all HIV+ subjects using flow cytometry.

13.8.1.5 Viral Serology

Viral serology testing will include HIV-1 and HIV-2 antibody, HBsAb, HBsAg, HBcAb, and HCV Ab. HCV titer will be confirmed by PCR for all subjects reported as HCV positive. All assessments will be performed at screening only, or if clinically indicated. A positive test for HBsAg will be repeated using a new blood sample.

13.8.2 Hematology, Clinical Chemistry and Lipid Panel

Hematology tests will be performed on EDTA-anticoagulated whole blood, and clinical chemistry assessments and the lipid panel will be performed on serum.

The hematology panel consists of complete blood count [hemoglobin, hematocrit, erythrocytes (i.e., red blood cell count), and leukocytes (i.e., white blood cell count)] with differential (i.e., basophils, eosinophils, lymphocytes, monocytes, neutrophils), mean corpuscular volume (MCV), mean corpuscular hemoglobin concentration (MCHC), and platelet count.

The clinical chemistry panel consists of sodium, potassium, chloride, bicarbonate, total protein, albumin, ALT, AST, total bilirubin, alkaline phosphatase, blood urea nitrogen, creatinine, and glucose.

The lipid panel consists of cholesterol, very low density lipoprotein (VLDL), low density lipoprotein (LDL), high density lipoprotein (HDL) and triglycerides.

13.8.3 FVIII Activity, FVIII Antigen, VWF Antigen

Blood samples will be analyzed for FVIII activity (1-stage clotting assay and the chromogenic assay) at a central laboratory. The 1-stage clotting assay will serve as the primary assay; the chromogenic assay will be used to provide supportive data. In addition FVIII antigen will be measured by ELISA. VWF antigen will be determined using ELISA from pre-infusion samples. The detailed timepoints of FVIII activity, FVIII antigen and VWF antigen assessment are provided in Section 12.1, Section 12.2, and Section 21.4.

13.8.4 Thrombin Generation Assay

For TGA parameters (lag time, time to peak thrombin generation, peak thrombin generation, and endogenous thrombin potential [ETP]), plasma samples will be tested using the calibrated, automated thrombin generation method (CAT). For details on the individual timepoints for TGA assessment please see Section 12.1, Section 21.2, and Section 21.4.

13.8.5 Assessment of Laboratory Values

13.8.5.1 Assessment of Abnormal Laboratory Values

The investigator's assessment of each laboratory value (i.e., hematology, clinical chemistry, and lipids) will be recorded on the CRF. For each abnormal laboratory value, the investigator will determine whether the value is considered clinically significant or not. For clinically significant values, the investigator will indicate if the value constitutes a new AE (see definition in Section 13.2, and record the sign, symptom, or medical diagnosis on the AE CRF), is a symptom or related to a previously recorded AE, is due to a pre-existing disease (described in Section 13.2.3), or is due to another issue that will be specified. If the abnormal value was not clinically significant, the investigator will indicate the reason, i.e., because it is due to a preexisting disease, due to a lab error, or due to another issue that will be specified. Additional tests and other evaluations required to establish the significance or etiology of an abnormal value, or to monitor the course of an AE should be obtained when clinically indicated. Any abnormal value that persists should be followed at the discretion of the investigator.

13.8.6 Biobanking

Subjects will consent for taking an extra blood sample at each study visit for additional analysis, if necessary. Backup samples that remain after study testing is done may be stored and used for additional testing (e.g., further evaluation of an abnormal test or an AE).

Also, an additional blood draw for further exploratory testing, i.e., biomarkers for hemophilia, will be drawn pre-infusion and early in the morning, if feasible, otherwise at the same timepoint at the Baseline, Month 3, Month 6, Month 9, and Completion/Termination study visit (see Clinical Laboratory Assessment Schedule in Section 21.4).

Samples will be stored in a coded form for no more than 2 years after the final study report has been completed and then the samples will subsequently be destroyed.

13.9 Vital Signs

Vital signs will include body temperature (°C or °F), respiratory rate (breaths/min), pulse rate (beats/min), and systolic and diastolic blood pressure (mmHg). Height (in or cm) and weight (lb or kg) will also be collected at screening; weight will also be recorded before any IP infusions are administered at the study site, but at least at each study visit. Blood pressure will be measured when subjects are in the supine position.

Vital signs will be assessed within 15 minutes prior to start of infusion and 30 ±5 minutes following infusion at baseline and at each study visit. Vital signs should always be assessed before any blood sampling is done at a particular timepoint.

Vital sign values are to be recorded on the CRF. For each abnormal vital sign value, the investigator will determine whether or not to report an AE (see definition in Section 13.2 and record the medical diagnosis (preferably), symptom, or sign on the AE CRF). Additional tests and other evaluations required to establish the significance or etiology of an abnormal value, or to monitor the course of an AE should be obtained when clinically indicated. Any abnormal value that persists should be followed at the discretion of the investigator.

14. STATISTICS

14.1 Sample Size and Power Calculations

14.1.1 Sample Size Calculation

For the sample size assessment the following assumptions were used. Approximately 40% of subjects in BAX 855 regimen targeting 1-3% trough level are expected to be bleed-free as shown in the ADVATE Prophylaxis study and the BAX 855 pivotal study 261201. For the BAX 855 regimen targeting approximately 10% (8-12%) trough level, an increase to 70% bleed-free subjects is expected based on modeling the bleeding rates per FVIII level in the BAX 855 pivotal study 261201.

Under these assumptions 48 subjects per study arm are needed to reject the null hypothesis of no difference between the study arms against a 2-sided alternative at the 5% level of statistical significance with 80% power. Assuming a drop-out rate of close to 10%, and 10-15% of subjects being non-compliant, approximately 116 subjects are planned to be randomized between the 2 BAX 855 regimens with an allocation ratio of 1:1.

14.2 Datasets and Analysis Cohorts

14.2.1 Full Analysis Set

The Full Analysis Set will comprise all subjects who were randomized and who were treated with BAX 855 prophylactically for any period of time.

14.2.2 Per Protocol Analysis Set

The Per Protocol Analysis Set will comprise all subjects who were randomized and completed the second 6 months of prophylactic treatment.

14.2.3 Safety Analysis Set

The Safety Analysis Set (SAS) will comprise all subjects treated with at least 1 BAX 855 dose. All safety analyses for BAX 855 will be performed on the SAS.

14.3 Handling of Missing, Unused, and Spurious Data

Missing data will not be imputed in general, with the exceptions as detailed below.

14.3.1 Handling of incomplete observation periods for ABR

The primary endpoint requires complete data for the second 6 months of prophylaxis (Day 183 to Day 364). The multiple imputations technique will be used for the analysis of the primary endpoint and estimation of ABRs. As this is a statistical analysis technique, it will be described in the statistical analysis section.

14.3.2 Handling of other variables

If body weight is missing for a subject then the last value of available body weight measurement will be carried forward in order to compute weight-adjusted BAX 855 consumption. If the date of onset for an AE is missing completely then it will be imputed with the date of the first study drug application.

For PK data, if any concentration data are considered spurious (e.g., lack of biological plausibility), the reason for exclusion and the analysis from which the data point was excluded will be documented.

Regarding missing data in AE records:

- Handling of unknown causality assessment:
 - If a subject experiences an AE with a missing causality assessment, the relationship of the AE will be counted as “related”.
- Handling of unknown severity grades:
 - If a subject experiences more than one AE categorized under the same preferred term, one of them is categorized as “severe” and one of them is categorized as “unknown”, the severity of this AE will be counted as “severe”.
- If a subject experiences more than one AE categorized under the same preferred term, one of them is categorized as “mild” or “moderate” and one of them is categorized as “unknown”, the severity of this AE will be counted as “unknown”.

14.4 Methods of Analysis

14.4.1 Primary Outcome Measure

The proportion of subjects with ABR = 0 in the 2 prophylaxis treatment regimens in the second 6 months period will be compared using a chi-square test with continuity correction at a 2-sided 5% level of significance.

The null hypotheses of no difference between the prophylactic regimens will be tested against a 2-sided alternative.

The observation period for the primary endpoint will be the second 6 months of prophylaxis (Day 183 to Day 364). If the subject undergoes a surgical procedure the observation period is interrupted starting from the presurgical loading dose until the subject resumes his previous prophylactic treatment regimen, or until rehabilitation or any other surgery specific postoperative measures have been completed, whichever occurs last.

Data analyses will follow the intent-to-treat principle, i.e., bleedings observed in the observation period will be used in the analyses irrespective of compliance with the treatment regimen of the protocol. Only if a subject refuses to provide any bleeding data, the multiple imputations (MI) technique will be used to handle observation periods shorter than 6 months, i.e., 182 days, as follows.

For subjects who terminated before Day 364 and refuse to provide data on bleeds, bleeds will be imputed for the unobserved period from a Poisson random variate. The subject specific Poisson parameter will be determined from estimating a negative binomial model for the bleed rate in the unobserved period with stratum, age, race as well as the number of bleeds from Day 92 to the end of the observed period of the subject as covariates in all subjects of the same Study Arm. For subjects with more than 21 weeks in the observation period, the number of bleeds occurring at a later time in other subjects might be very low or even zero. To avoid estimating from an unstable model, the negative binomial model will be for the number of bleed up to Day 329 with covariates of stratum, age, race and number of bleeds observed from Day 92 to Day 329. At least 1000 imputation datasets will be generated. The chi-squared test statistics with continuity correction and its standard error will be used to compare the 2 study arms in each imputation dataset and the multiple imputations techniques will be used to derive an overall estimate with 2-sided 95% CIs.

The dataset to be analyzed is all subjects. For subjects who developed an inhibitor, missing observation periods will be imputed at twice the rate before the study.

The use of age and race in the imputation model will allow for subgroup analyses of the primary endpoint and ABRs.

Sensitivity analyses

Sensitivity analyses will be performed similar to the primary analysis except that the negative binomial distributions used for imputations will have an artificially increased Poisson parameter by 10%, 20%, 40% and 80%. In addition, a worst-case sensitivity analysis will be performed which imputes worst-case outcomes in all subjects with missing ABR data in the observation period.

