5.5.1.1 Primary Endpoint Imputation

The unobserved period (which is subject specific), is defined as the subject's missing observation period in PROPEL for which there is no post-PROPEL bleed information provided.

Step1: Fitting the model

- A subject specific Negative Binomial model will be fitted. The dependent variable (left-side of the model equation), is the number of bleeds in the subject's unobserved period after ObsDay 182, taken from all subjects in the same treatment arm (low level or high level), as the subject being imputed. The offset will be the logarithm of the duration (in days), of the unobserved period for the subject (LUP). Covariates (model variables) will be stratum category, race, age at baseline and total number of bleeds observed per subject (OB), calculated for all subjects in the same treatment group of the subject for imputation.

- It is desired to avoid using bleeds in the endmost observation period as part of the covariates since the number of bleeds observed in other subjects at that time might be very low or even zero. Therefore OB, is measured in the range from ObsDay 92 up to the minimum of:
 - Last ObsDay for subject being imputed.
 - ObsDay 329.
- The following example SAS[®] code can be utilized:

```
Proc Genmod Data = <Dataset>;  
  Class <Stratn> <Racen>;  
  Model <UB> = <Stratn> <Racen> <BAge> <OB> / Dist = Negbin  
    Offset = <LUP> Link = log;  
  ODS Output ParameterEstimates = <Outdata>  
Run ;
```

Where <Dataset> represents the input dataset containing all subjects in the same treatment arm as the subject being imputed, who have at least the same amount of ObsDays as the subject being imputed. <UB> represents the number of bleeds during the subject's unobserved period (up to the maximum of ObsDay 329), <Stratn> is the numeric stratum category, <Racen> the numeric race category, <BAge> the age at baseline, <OB> and <LUP> as defined above and <OutData> the output dataset containing the parameter estimates.

Step2: Predicting the Poisson Parameter and Imputing with it

- The subject-specific Poisson parameter will be predicted from the above model fitting results by using the predicted mean number of bleeds during the subject's unobserved period (Mu) as the prediction for the Poisson parameter.
- The number of bleeds for the subject to be imputed, will be for the "imputation period" (days), where the imputation period is defined as:

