Imputation Period (days) = (Date Corresponding to ObsDay 364 – Imputation Start Date)

Where imputation start date is as defined in section 5.4.2: Extended Observation Period of Efficacy.

- This “imputation period” will be treated/imputed as a Poisson random variate. The following example SAS[®] code can be utilized to obtain an estimate for the Poisson parameter:

```
Data <ImpSet>;  
  Set <Dataset>;  
  
  <Mu> = exp(1*<Intcpt> + <Beta1>*<sStrat> + <Beta2>*<sRace> +  
            <Beta3>*<sBAge> + <Beta4>*<sOB> + <LIP>);  
  Do i = 1 to 1 000  
    <ImpUB> = Ranpoi(1234,mu);  
    Iteration = i;  
    Output;  
  End;  
Run;
```

Where <Impset> represents the resultant dataset containing the 1 000 imputed bleed count values. <Dataset> is the input dataset containing the parameter estimates obtained from fitting the Negative binomial as discussed above and <Mu> our Poisson parameter as defined above. <Beta1>, <Beta2>, <Beta3> and <Beta4> the parameter estimates for <Stratn>, <Racen>, <BAge> and <OB> respectively. <sStratn>, <sRacen>, <sBAge> and <sOB> hold values specific to the subject being imputed, for numeric stratum category, numeric race category, baseline age and observed bleeds from ObsDay92 till last ObsDay for the subject, respectively. <LIP> is the logarithm of the imputation period (days) for the subject being imputed and <ImpUB> is the imputed number of bleeds during the imputation period for the subject.

Step3: Adding of Imputed Values to the Observed Values

The imputed bleed count of the subject is added to the subject’s observed bleed count (i.e. the subject’s observed bleeds after ObsDay 182), to obtain a bleed count for the complete 2nd 6-month period of the subject.

$$\text{Complete period bleeds} = \text{Observed period bleeds} + \text{Bleeds for imputation period}$$

For each subject to be imputed, the 1 000 imputed values will be merged into the full subject dataset, thus creating 1 000 replicates of imputed (complete) data sets (one for each imputation iteration).

Step4: Calculating ABR and Categorization

From this step onward we are working with all the subjects (those imputed and those not needing imputation) in the same dataset (1 000 replicates of them).

ABR is calculated as:

$$ABR = \frac{(Observed\ Number\ of\ bleeds + Imputed\ number\ of\ bleeds)}{Period\ under\ consideration\ in\ years}$$

Where period under consideration is:

- 1 year (365.2425 days) when working with the full year.

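### Missing bleed counts are drawn from a Poisson at the negative binomial mean, so imputed subjects are bleed-free too rarely; at the planned rates this modestly widens the primary difference, under conditions

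*Protocol*

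**What the plan says.** Protocol 14.4.1 imputes only for subjects who stop before Day 364 and decline to give bleed data. For them, "bleeds will be imputed for the unobserved period from a Poisson random variate". The Poisson parameter comes from a negative binomial model fitted within the subject's own arm, with stratum, age, race and earlier bleeds as covariates.

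SAP 5.5.1.1 gives the operational version. In Step 1, "A subject specific Negative Binomial model will be fitted". In Step 2 the exponentiated linear predictor becomes the Poisson parameter, and the imputation period "will be treated/imputed as a Poisson random variate". The sample code passes that mean straight to the SAS Poisson generator. The dispersion estimated in Step 1 is not used again, and the regression coefficients are held at their estimates across all 1,000 imputations. In Step 3 the imputed count is added to any bleeds observed in the window.

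The sensitivity paragraph of protocol 14.4.1 refers to "the negative binomial distributions used for imputations", yet inflates a Poisson parameter. SAP 5.5.1.2 applies the 10%, 20%, 40% and 80% inflations to the Poisson parameter in both arms. SAP 5.5.1.3 carries the same procedure to the secondary bleeding outcomes.

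**The concern.** A negative binomial is fitted when counts vary more than a Poisson allows. A draw from a Poisson at the fitted mean removes that extra variation from the imputed values. For an endpoint based on the mean count this would matter little. For an endpoint defined by zero bleeds it matters directly: at a given mean, overdispersed counts contain more zeros.

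At stake is the primary comparison. If the zero probability is understated by different amounts in the two arms, the imputed subjects shift the estimated difference. None of the planned sensitivity analyses would show this. Inflating the mean, or imputing the worst case, lowers the imputed bleed-free share further. Removing post-study bleed data imputes more person-time with the same Poisson draw. No planned analysis restores the overdispersion.

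**Working it through.** **Planned rates and test.** From protocol 14.1.1: "Approximately 40% of subjects in BAX 855 regimen targeting 1-3% trough level are expected to be bleed-free" and, in the other arm, "an increase to 70% bleed-free subjects is expected", tested "at the 5% level of statistical significance with 80% power". The test in 14.4.1 is a "chi-square test with continuity correction at a 2-sided 5% level of significance". The usual two-proportion formula for 0.40 against 0.70 gives 42 per arm without continuity correction and 49 with it. Exact power of the corrected test at 48 per arm is 80.05%, so the plan's 48 is reproduced. The rates 0.40 and 0.70 are used below.

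**Zero probabilities.** With mean m and dispersion k:

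- Negative binomial: P(0) = (1 + km)^(-1/k)
- Poisson with the same mean: P(0) = exp(-m)

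For any k > 0 the second is smaller. The documents give no k for this trial, so k is an assumption and a range is shown. For each k, m is set so that the negative binomial returns the planned rate: m = (P0^(-k) - 1)/k. At k = 1 this gives m = 1/0.40 - 1 = 1.5 and m = 1/0.70 - 1 = 0.429. The Poisson draw then gives exp(-1.5) = 0.223 and exp(-0.429) = 0.651.

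| k (assumed) | Low arm: m | Poisson P(0) | Shortfall from 0.40 | High arm: m | Poisson P(0) | Shortfall from 0.70 | Widening, 10% per arm imputed for whole window |
|---|---|---|---|---|---|---|---|
| 0.25 | 1.030 | 0.357 | 0.043 | 0.373 | 0.689 | 0.011 | 0.3 points |
| 0.5 | 1.162 | 0.313 | 0.087 | 0.390 | 0.677 | 0.023 | 0.6 points |
| 1 | 1.500 | 0.223 | 0.177 | 0.429 | 0.651 | 0.049 | 1.3 points |
| 2 | 2.625 | 0.072 | 0.328 | 0.520 | 0.594 | 0.106 | 2.2 points |

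The last column is 10% of the difference between the two shortfalls; at k = 1, 0.10 × (0.177 - 0.049) = 0.0128.

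**Half the window missing.** Halve m and apply the shortfall to all of the 10%, although those who had already bled would be unaffected. At k = 0.5 the shortfalls are 0.041 and 0.007, so 0.10 × 0.034 = 0.3 points. At k = 1 they are 0.099 and 0.016, so 0.10 × 0.083 = 0.8 points. At k = 2 they are 0.256 and 0.040, so 0.10 × 0.216 = 2.2 points: at that dispersion, halving the window does not by itself reduce the figure.

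**When the direction changes.** The models are fitted by arm, so k and missingness can differ.

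- Low-arm k of 0.5 and high-arm k of 2: the low-arm shortfall minus the high-arm shortfall is -1.8 points among imputed subjects. With k of 1 and 3 it is +0.5, close to break-even. Reversal therefore needs about a 3- to 4-fold larger dispersion in the high arm.
- Common k = 1: reversal needs missingness in the high arm above 0.177/0.049 = 3.6 times that in the low arm.

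**Effect on the test.** A simulation used 58 per arm, 200 imputations, known m and k, the whole window missing at random, and the signed root of the corrected chi-square combined as in SAP Steps 5 and 6.

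- 40% against 70%, k = 1, 10% missing: mean difference 0.311 with the Poisson draw against 0.300 with the negative binomial draw; apparent power 90% against 87%.
- 40% in both arms, k = 1, 17.2% missing in each: mean difference about zero, rejection 1.5% against 1.0%.
- 40% in both arms, k = 1, 5% missing in the low arm and 25% in the high arm: a spurious difference of -3.4 points against the arm with more missing data, rejection 2.3%.

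**The case against.** **The protocol could be read more kindly.** A subject-specific Poisson parameter taken from a negative binomial model, together with the sensitivity paragraph's reference to negative binomial distributions, is compatible with a gamma-mixed Poisson. That stands for the protocol alone. The SAP code rules it out, so the point rests mainly on SAP Step 2.

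**The bias need not favour the high-trough arm.** A reader might infer that it always does, because the gap between the two zero probabilities grows with the mean. It does not grow without limit. At k = 1 it is 0.177 at m = 1.5, 1/3.5 - exp(-2.5) = 0.204 at m = 2.5, and 1/6 - exp(-5) = 0.160 at m = 5. Imputed means depend on earlier bleeds, so heavy bleeders may lie past the peak. The ordering holds at the planned rates with a common k and similar missingness, not in general.

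**Few subjects are exposed.** Taking 10% as imputed treats the whole planned dropout as refusing to give bleed data. Data from the continuation study or from the subject count as observed (SAP 7.1.2.1 and 7.1.2.2), anyone who already bled in the window is unaffected, and the covariates may absorb part of the dispersion. All of this stands. A reader might also use 17.2%, from (116 - 96)/116, but that allowance includes non-compliant subjects, whose observed bleeds the intent-to-treat rule in protocol 14.4.1 keeps.

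**The dispersion is unknown.** The pediatric results in protocol 6.4.2 (mean ABR 3.04, 37.9% bleed-free) imply k of about 0.87 if six months of observation is assumed. That is a marginal value in children under 12, not the residual dispersion of this model, and it should not be taken as the trial's k.

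**The worst-case analysis pushes the other way.** If every imputed subject counts as a bleeder and 10% are missing, the low arm loses 4 points and the high arm 7, so the difference shrinks by 3. This is a useful bound, but it does not correct the draw, and SAP 5.5, to which 7.1.2 refers for it, does not define it.

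**Conclusion.** The point holds in a conditional form. The draw discards the estimated dispersion, so with any overdispersion the imputed probability of no bleeds is too low. That part is mathematical and needs no assumption about size.

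The effect on the arm difference does need assumptions. At 40% against 70%, with similar dispersion and missingness in both arms, the shortfall is larger in the low-trough arm and the difference widens modestly. The 0.3 to 2.2 points for k of 0.25 to 2 is an upper end, not an expected value: it needs 10% per arm imputed for the whole window. With half the window missing it is about 0.3 to 0.8 points for k of 0.5 to 1. It is smaller still where subjects supply post-study data, have already bled in the window, or where covariates absorb dispersion.

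A reader might infer a false-positive problem. The simulation does not support that: with equal rates and equal missingness the rejection rate stayed well below 5%. The change should be made because it removes a known bias from the primary analysis at little cost, not because the trial's conclusion is likely to turn on it.

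**What to change.** In SAP 5.5.1.1 Step 2, draw each imputed count from the fitted negative binomial: a gamma variate with the predicted mean and the dispersion estimated in Step 1, then a Poisson draw at that value. Preferably, also draw the model parameters afresh for each imputation, so that their uncertainty is carried through and the imputation is proper.

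Prespecify a fallback for an arm-specific dispersion estimate that is unstable or on the boundary, for example a dispersion pooled across arms. Each fit uses one arm of about 58 subjects with several covariates, and the protocol itself already guards against an unstable model late in the window.

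Align the wording in three places: the draw in protocol 14.4.1, the sensitivity paragraph of the same section, and SAP 5.5.1.2, so that the inflations act on the negative binomial mean.

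The cost is a little extra programming, a few sentences of text and slightly more imputation variance.
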